6.6.1.3 Guidelines for Dose Modification: Specific Hematologic Toxicities

Consider use of granulocyte colony stimulating factor (G-CSF) as per institutional guidelines or as per ASCO guidelines for neutropenia/febrile neutropenia. Prophylactic G-CSF may not be used during the first cycle of camidanlumab tesirine.

For anemia, consider use of erythropoietin as per institutional guidelines.

6.6.1.4 Guidelines for Dose Modification: Specific Neurologic Toxicities

Patients experiencing any new neurological toxicities and/or new onset of pain refractory to common pain medications \geq Grade 1, not explained by previous medical history, that could be linked to or may be an early indicator of polyradiculopathy/GBS, such as ascending (bilateral) sensory loss or motor weakness, need to be immediately evaluated by a neurologist and dosing of camidanlumab tesirine must be held until polyradiculopathy/GBS is ruled out. Please refer to Section 6.9.6 for management of polyradiculopathy/GBS, especially for the recommendation of prompt initiation of therapy upon reasonable suspicion of polyradiculopathy/GBS. Should further clinical, radiologic, or laboratory evidence support the diagnosis of polyradiculopathy/GBS with level 1 diagnostic certainty (Section 6.9.6 and Appendix 13.3), treatment with camidanlumab tesirine must be permanently discontinued.

Patients with \geq Grade 3 neurologic toxicities defined as peripheral sensory and peripheral motor neuropathies, and not explained by previous medical history, must have treatment with camidanlumab tesirine permanently discontinued.

Other new neurological findings not explained by previous medical history with an increase of ≥ 1 grade over Baseline will result in dose delay; dosing may be resumed after resolution to Baseline, at the investigator's discretion. The patient must be carefully monitored at least weekly until such resolution (can be done by telephone unless symptoms worsen).

6.6.1.5 Guidelines for Dose Modification: Specific Skin Toxicities

Adverse Event	Grade	Camidanlumab Tesirine Management Guideline
Maculopapular rash or Photosensitivity rash or Pruritus	1	No dose adjustment is required and monitor for change in severity. Topical treatment to affected areas is indicated: 
- maculopapular rash, photosensitivity rash, or pruritus: high potency topical steroid cream BID (e.g., clobetasol propionate 0.05%, halobetasol propionate 0.05%).- xerosis or hyperpigmentation: consider ammonium lactate 12% or urea 20% BID. Reassessment every 2 weeks is indicated (either by healthcare professional or patient self-report).
Xerosis	2	No dose adjustment is required and monitor for change in severity. Topical treatment to affected areas is indicated: 
- maculopapular rash or photosensitivity rash: high potency topical steroid cream BID (e.g., clobetasol propionate 0.05%, halobetasol propionate 0.05%).

Adverse Event	Grade	Camidanlumab Tesirine Management Guideline
or Hyperpigmentation		
 - pruritus: high potency topical steroid cream BID and consider oral antipruritic (e.g., hydroxyzine, gabapentin, or pregabalin). - xerosis or hyperpigmentation: consider ammonium lactate 12% or urea 20% BID. 
Reassessment every 2 weeks is indicated (either by healthcare professional or patient self-report).
 
In case these Grade 2 rashes become intolerable, Grade 3 recommendations may be applied.

	3	
Hold camidanlumab tesirine until improvement to \leqGrade 1 or Baseline and consider dermatology consult.
 
Topical treatment to affected areas is indicated and consider systemic corticosteroid treatment e.g., prednisone 0.5 mg/kg for 10 days:
 
 - maculopapular rash or photosensitivity rash: high potency topical steroid cream BID (e.g., clobetasol propionate 0.05%, halobetasol propionate 0.05%) and consider prednisone 0.5 mg/kg for 10 days. - pruritus: high potency topical steroid cream BID (e.g., clobetasol propionate 0.05%, halobetasol propionate 0.05%) and consider oral antipruritic (e.g., hydroxyzine, gabapentin, or pregabalin). - xerosis or hyperpigmentation: consider ammonium lactate 12% or urea 20% BID; and triamcinolone 0.1% cream BID. 
Reassessment every 2 weeks is indicated (either by healthcare professional or patient self-report); if reactions do not improve, then:
 
First Occurrence:
 
 • If improvement to \leqGrade 1 or Baseline occurs prior to the next scheduled dose, proceed with the originally planned camidanlumab tesirine dose level. • If improvement to \leqGrade 1 or Baseline occurs >21 days from the last scheduled (but missed) camidanlumab tesirine dose, reduce by 1 dose level from the original assigned dose in subsequent treatment cycles. 
Second Occurrence:
 
 • If improvement to \leqGrade 1 or Baseline occurs prior to the next scheduled dose, reduce by 1 dose level from the original assigned dose in subsequent treatment cycles. • If improvement to \leqGrade 1 or Baseline occurs >21 days from the last scheduled (but missed) camidanlumab tesirine dose, reduce by 2 dose levels from the original assigned dose in subsequent treatment cycles.

Adverse Event	Grade	Camidanlumab Tesirine Management Guideline
	4	
 Otherwise, camidanlumab tesirine should be permanently discontinued. 
Third Occurrence: Permanently discontinue camidanlumab tesirine.
 
Hold camidanlumab tesirine until improvement to \leqGrade 1 or Baseline and consider dermatology consult.
 
Topical treatment to affected areas is indicated and consider systemic corticosteroid treatment e.g., prednisone 0.5 mg/kg for 10 days:
 
 maculopapular rash or photosensitivity rash: high potency topical steroid cream BID (e.g., clobetasol propionate 0.05%, halobetasol propionate 0.05%) and consider prednisone 0.5 mg/kg for 10 days. pruritus: high potency topical steroid cream BID (e.g., clobetasol propionate 0.05%, halobetasol propionate 0.05%) and consider oral antipruritic (e.g., hydroxyzine, gabapentin, or pregabalin). xerosis or hyperpigmentation: consider ammonium lactate 12% or urea 20% BID; and triamcinolone 0.1% cream BID. 
Reassessment every 2 weeks is indicated (either by healthcare professional or patient self-report); if reactions do not improve, then:
 
First Occurrence:
 
 If improvement to \leqGrade 1 or Baseline occurs prior to the next scheduled dose, continue camidanlumab tesirine and reduce by 1 dose level from the original assigned dose in subsequent treatment cycles. If improvement to \leqGrade 1 or Baseline occurs >21 days from the last scheduled (but missed) camidanlumab tesirine dose, reduce by 2 dose levels from the original assigned dose in subsequent treatment cycles. Otherwise, camidanlumab tesirine should be permanently discontinued. 
Second Occurrence: Permanently discontinue camidanlumab tesirine.

Blistering rash	1	
No dose adjustment is required and monitor for change in severity. Consider dermatology consult
 
Topical treatment to affected areas is indicated, e.g., silvadene 1% cream BID and consider laboratory testing for blistering disorder (VZV/HSV and bacterial infection; bullous pemphigoid; pemphigus).
 
Reassessment every 2 weeks is indicated (either by healthcare professional or patient self-report).

Adverse Event	Grade	Camidanlumab Tesirine Management Guideline
	2/3	
Hold camidanlumab tesirine until improvement to \leqGrade 1 or Baseline and consider dermatology and wound care consult. Topical treatment to affected areas is indicated, e.g., silvadene 1% cream bid, and consider laboratory testing for blistering disorder (VZV/HSV and bacterial infection; bullous pemphigoid; pemphigus) and consider systemic corticosteroid treatment e.g., prednisone 0.5 mg/kg for 10 days. Reassessment every 2 weeks is indicated (either by healthcare professional or patient self-report); if reactions do not improve, then:
 
First Occurrence:
 
 • If improvement to \leqGrade 1 or Baseline occurs prior to the next scheduled dose, proceed with the originally planned camidanlumab tesirine dose level. • If improvement to \leqGrade 1 or Baseline occurs >21 days from the last scheduled (but missed) camidanlumab tesirine dose, reduce by 1 dose level from the original assigned dose in subsequent treatment cycles. • Otherwise, camidanlumab tesirine should be permanently discontinued. 
Second Occurrence:
 
 • If improvement to \leqGrade 1 or Baseline occurs prior to the next scheduled dose, reduce by 1 dose level from the original assigned dose in subsequent treatment cycles. • If improvement to \leqGrade 1 or Baseline occurs >21 days from the last scheduled (but missed) camidanlumab tesirine dose, reduce by 2 dose levels from the original assigned dose in subsequent treatment cycles. • Otherwise, camidanlumab tesirine should be permanently discontinued. 
Third Occurrence:
 
Permanently discontinue camidanlumab tesirine.

	4	
Hold camidanlumab tesirine until improvement to \leqGrade 1 or Baseline and consider dermatology consult. Topical treatment to affected areas is indicated, e.g., silvadene 1% cream BID, and consider laboratory testing for blistering disorder (VZV/HSV and bacterial infection; bullous pemphigoid; pemphigus) and consider systemic corticosteroid treatment, e.g., prednisone 0.5 mg/kg for 10 days. Reassessment every 2 weeks is indicated (either by healthcare professional or patient self-report); if reactions do not improve, then:

Adverse Event	Grade	Camidanlumab Tesirine Management Guideline
		
First Occurrence:
 
 • If improvement to \leqGrade 1 or Baseline occurs prior to the next scheduled dose, continue camidanlumab tesirine and reduce by 1 dose level from the original assigned dose in subsequent treatment cycles. • If improvement to \leqGrade 1 or Baseline occurs >21 days from the last scheduled (but missed) camidanlumab tesirine dose, reduce by 2 dose levels from the original assigned dose in subsequent treatment cycles. • Otherwise, camidanlumab tesirine should be permanently discontinued. 
Second Occurrence:
 
Permanently discontinue camidanlumab tesirine.

Abbreviations: BID=twice daily; HSV=herpes simplex virus; VZV=varicella zoster virus

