6.4 Camidanlumab Tesirine Combination with Pembrolizumab Dosing

In the dose-escalation portion of the study (Part 1), the initial dose of camidanlumab tesirine will be 30 µg/kg (Dose Level 1) every 3 weeks (Q3W) for 2 cycles (on C1D1 and C2D1). The maximum dose possibly administered will be the highest dose of camidanlumab tesirine as monotherapy investigated and deemed to be safe. The dose-escalation procedure is described in Section 4.1.1.

Pembrolizumab at dose of 200 mg Q3W will be administered on Day 1 of each cycle starting from Cycle 1 onwards (dosing schedule 1).

If unacceptable toxicity (Section 6.5) occurs during Cycle 1 at dose level -1 and dose level -2, dosing Schedule 2, where pembrolizumab administration may start at Cycle 2, may be investigated in new enrolled patients.

Patients who tolerate the study treatment (i.e., no liver enzyme increase \geq Grade 2, no pleural effusion \geq Grade 2, no edema \geq Grade 2) and are in disease control (defined as disease control \geq SD) may receive additional doses of camidanlumab tesirine in combination with pembrolizumab, upon informing the Sponsor.

Additional administrations of camidanlumab tesirine in combination with pembrolizumab will be given as follows: 2 consecutive Cycles every 2 Cycles (2 cycles on, 2 cycles off schedule),

starting from Cycle 5 up to a year (i.e., Cycle 5 and 6, Cycle 9 and 10, Cycle 13 and 14, Cycle 17 and 18) if there is no delay in the planned treatment schedule: Between these cycles, patients should receive pembrolizumab as a single agent.

In case of delay in the administration of pembrolizumab, additional administrations of camidanlumab tesirine can be done after respecting a minimum of 63 days (9 weeks) between the last dose of camidanlumab tesirine and the first dose of the 2 subsequent additional administrations of camidanlumab tesirine.

Study treatment is given up to a year. Continued administration of camidanlumab tesirine as monotherapy or camidanlumab in combination with pembrolizumab, or pembrolizumab alone after a year is to be discussed with the Sponsor.

A patient should maintain the same treatment schedule throughout the duration of the trial. However, once RDE is identified, patients receiving lower or higher dose levels of camidanlumab tesirine enrolled in Part 1 may be offered continued treatment at RDE.

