6.6 Dose Delays and Modifications

When both camidanlumab tesirine and pembrolizumab have been dosed and an AE occurs with relationship to study treatment and requires study treatment hold, the resumption of study treatment can occur only with one study drug at a time. The second study drug may be resumed at the next planned Cycle.

In the above situation, prior to the resumption of any study drugs, discussion should occur with the Sponsor.

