6.6.1.1 Camidanlumab Tesirine Dose Modification Guidelines: General Toxicities

AE Grade	Camidanlumab Tesirine Management Guideline
1/2	No dose adjustment is required.
3/4	
First Occurrence:
 
Hold camidanlumab tesirine until improvement to \leqGrade 1 or Baseline.
 
If improvement to \leqGrade 1 or Baseline occurs prior to the next scheduled dose, continue camidanlumab tesirine at the original assigned dose level in subsequent treatment cycles.
 
If improvement to \leqGrade 1 or Baseline occurs >21 days from the last scheduled (but missed) camidanlumab tesirine dose, continue camidanlumab tesirine and reduce by 1 dose level from the original assigned dose in subsequent treatment cycles.
 
Second Occurrence:
 
Hold camidanlumab tesirine until improvement to \leqGrade 1 or Baseline.
 
If improvement to \leqGrade 1 or Baseline occurs prior to the next scheduled dose, reduce by 1 dose level from the original assigned dose in subsequent treatment cycles.
 
If improvement to \leqGrade 1 or Baseline occurs >21 days from the last scheduled (but missed) camidanlumab tesirine dose, continue camidanlumab tesirine and reduce by 2 dose levels from the original assigned dose in subsequent treatment cycles.
 
Otherwise, camidanlumab tesirine should be permanently discontinued.
 
Third Occurrence:
 
Permanently discontinue camidanlumab tesirine.

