AST, ALT, or GGT abnormalities or Edema or Effusion	2/3	
First Occurrence: Hold camidanlumab tesirine until improvement to \leqGrade 1 or Baseline.
 
If improvement to \leqGrade 1 or Baseline occurs prior to the next scheduled dose, continue camidanlumab tesirine at the original assigned dose level in subsequent treatment cycles.
 
If improvement to \leqGrade 1 or Baseline occurs >21 days from the last scheduled (but missed) camidanlumab tesirine dose, continue camidanlumab tesirine and reduce by 1 dose level from the original assigned dose in subsequent treatment cycles.
 
Second Occurrence: Hold camidanlumab tesirine until improvement to \leqGrade 1 or Baseline.
 
If improvement to \leqGrade 1 or Baseline occurs prior to the next scheduled dose, reduce by 1 dose level from the original assigned dose in subsequent treatment cycles.
 
If improvement to \leqGrade 1 or Baseline occurs >21 days from the last scheduled (but missed) camidanlumab tesirine dose, continue camidanlumab tesirine and reduce by 2 dose levels from the original assigned dose in subsequent treatment cycles.
 
Otherwise, camidanlumab tesirine should be permanently discontinued.
 
Third Occurrence: Permanently discontinue camidanlumab tesirine.

Adverse Event	Grade	Camidanlumab Tesirine Management Guideline
	4	
First Occurrence:
 
Hold camidanlumab tesirine until improvement to \leqGrade 1 or Baseline.
 
If improvement to \leqGrade 1 or Baseline occurs prior to the next scheduled dose, continue camidanlumab tesirine and reduce by 1 dose level from the original assigned dose in subsequent treatment cycles.
 
If improvement to \leqGrade 1 or Baseline occurs >21 days from the last scheduled (but missed) camidanlumab tesirine dose, continue camidanlumab tesirine and reduce by 2 dose levels from the original assigned dose in subsequent treatment cycles.
 
Otherwise, camidanlumab tesirine should be permanently discontinued.
 
Second Occurrence:
 
Permanently discontinue camidanlumab tesirine.

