6.6.1.5.1 Severe Immune-Mediated Skin Adverse Events

When a patient is treated with camidanlumab tesirine in combination with pembrolizumab, and there are cases of severe immune-mediated skin adverse events related to camidanlumab tesirine, the following recommendations for camidanlumab tesirine should be followed. These recommendations align with current guidances provided in the pembrolizumab prescribing information:

- Grade 3 immune-mediated skin AE, drug reaction with eosinophilia and systemic symptoms (DRESS), suspected Stevens-Johnson syndrome (SJS), suspected toxic epidermal necrolysis (TEN): withhold treatment regimen
- Grade 4 immune-mediated skin AE, DRESS, confirmed SJS, confirmed TEN: treatment regimen permanently discontinued

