6.6.1.6 Principles of Camidanlumab Tesirine Rechallenge

Exercise caution when considering resumption of camidanlumab tesirine after significant immune-related adverse events (irAEs) (\geq Grade 2). Close follow-up should be performed when resuming camidanlumab tesirine to monitor recurrent symptoms:

- If re-challenged and toxicity returns, permanently discontinue camidanlumab tesirine
- Assess patient's tumor status prior to rechallenge. If an objective response (complete or partial) to camidanlumab tesirine was achieved, resumption of camidanlumab tesirine may not be advisable due to risk of toxicity recurrence. Risks/benefits of restarting camidanlumab tesirine is to be discussed with Sponsor.

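### Protocol Section 6.6.1.5 puts the dose steps for held rashes under a non-improvement condition; read literally, an improved Grade 4 or recurrent rash has no stated reduction or discontinuation (minor safety-wording correction)

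*Protocol*

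**What the plan says.** Section 6.6.1.5 has four rows that hold camidanlumab tesirine until the reaction improves to Grade 1 or Baseline. Two cover maculopapular or photosensitivity rash, pruritus, xerosis and hyperpigmentation, at Grade 3 and at Grade 4. Two cover blistering rash, at Grade 2/3 and at Grade 4. Each then calls for reassessment every 2 weeks ("either by healthcare professional or patient self-report); if reactions do not improve, then") and lists first, second and, at the lower grades, third occurrence steps. The timed steps depend on when improvement occurs. At a first Grade 4 rash that improves before the next scheduled dose, for example, the instruction is to "continue camidanlumab tesirine and reduce by 1 dose level from the original assigned dose in subsequent treatment cycles".

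The parallel tables go straight from the hold to nearly the same steps. In Section 6.6.1.1, a first Grade 3/4 toxicity that improves before the next dose leads to the instruction to "continue camidanlumab tesirine at the original assigned dose level in subsequent treatment cycles". In Section 6.6.1.2 (liver enzymes, edema, effusion), a second Grade 2/3 occurrence that improves in time leads to "reduce by 1 dose level from the original assigned dose in subsequent treatment cycles". Neither table has a non-improvement condition.

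**The concern.** Steps that apply on improvement sit under a condition of non-improvement. A site that follows the words finds no step for a rash that has improved at the 2-week check. For a first Grade 3 (or blistering Grade 2/3) rash that improves before the next dose this changes nothing, because dosing resumes at the original level anyway. For a Grade 4 or recurrent rash, the missing step is a reduction or a permanent discontinuation.

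The stake is the dose given after a severe skin reaction to a PBD conjugate. Section 1.3 lists skin toxicity as an important potential risk.

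**Working it through.** The question is mainly textual; the arithmetic only bounds its reach.

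**1. What the lead-in removes.** Stated step when the rash improves before the next scheduled dose:

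| Row | 1st occurrence | 2nd | 3rd |
|---|---|---|---|
| Non-blistering, Grade 3 | original dose | down 1 level | stop |
| Non-blistering, Grade 4 | down 1 level | stop | – |
| Blistering, Grade 2/3 | original dose | down 1 level | stop |
| Blistering, Grade 4 | down 1 level | stop | – |

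Of the 10 entries, 2 keep the original dose. The other 8 (4 reductions, 4 discontinuations) do not apply, on the literal reading, to a rash improved at the check.

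**2. Whether another rule supplies the step.**
- Section 6.6.1.1 covers only toxicities not specified in the later sections, so it does not govern these rashes.
- Section 6.6.1 leaves resumption after any suspension to the Investigator and sets no dose.
- Section 6.5 makes most non-hematologic toxicity of Grade 3 or higher in the 21-day window a DLT in Part 1 escalation. Continuing then needs consultation with the Sponsor; no dose is set.
- Section 6.6, for a combination hold, resumes one drug at a time and says "prior to the resumption of any study drugs, discussion should occur with the Sponsor". No dose is set.
- Section 6.4 opens extra camidanlumab tesirine from Cycle 5 to "Patients who tolerate the study treatment (i.e., no liver enzyme increase" of Grade 2 or higher, with pleural effusion and edema as the other tests. Rash is not named. The Sponsor must be informed.
- Section 6.6.1.5.1, for the combination only, does set a rule: "Grade 4 immune-mediated skin AE, DRESS, confirmed SJS, confirmed TEN: treatment regimen permanently discontinued". Section 6.6.1.6, on resuming after significant immune-related events, adds "If re-challenged and toxicity returns, permanently discontinue camidanlumab tesirine". Neither says whether an ordinary rash counts as immune-related. Section 8.1.1 says that rashes generally do not, but only in defining AESIs.
- Appendix 13.4 was not in the text available for this review and may add cover for immune-related events.

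**3. Timing in the combination** (SAP Table 1: camidanlumab tesirine on days 1, 22 and 85; check taken as 14 days after onset).
- Gap after Cycle 1: 22 − 1 = 21 days. The check falls by the next dose if onset is within 21 − 14 = 7 days.
- Gap after Cycle 2: 85 − 22 = 63 days. The check falls by the next dose if onset is within 63 − 14 = 49 days.

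The case therefore arises mainly for re-dosing at Cycle 5. With one occurrence per dose, a third occurrence cannot precede the Cycle 5 dose, so the third-occurrence entries are remote.

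**4. Size of a missed reduction** (Protocol Table 5, levels 1 to 7; 150 µg/kg is the highest monotherapy dose reported in Section 1.3.4). One level down is (30 − 20)/30 = 33.3%, (45 − 30)/45 = 33.3%, 25% from 60 or 80, 20% from 100 or 125, and (150 − 125)/150 = 16.7%.

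**5. Patients.** Section 1.3.4 reports Grade 3 or higher rash in 6.8% of 44 monotherapy patients: 3/44, exact 95% CI 1.43% to 18.66%. Planned combination patients: 65 − 44 + 30 = 51, if Part 1 fills and all 44 count within it. Expected with any Grade 3 or higher rash: 51 × 0.0682 = 3.5, range 51 × 0.0143 = 0.7 to 51 × 0.1866 = 9.5. Those affected are the Grade 4 or recurrent cases that have also improved by the check and are re-dosed. Any recurrent Grade 2 blistering rash, or recurrent intolerable Grade 2 rash handled as Grade 3, would add to them. The documents give no counts for these.

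**The case against.** The strongest reply is that this is a slip whose meaning is obvious. Every timed step opens with improvement, and the steps mirror the parallel tables. For a rash starting more than 7 days after the Cycle 1 dose, the literal reading leaves the step for improvement before the next dose almost nothing to act on. Many investigators would apply the table as intended. This stands, and it is why the point is minor.

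A reader might infer that the protocol directs full-dose re-dosing after a Grade 4 or recurrent rash. The documents do not support that. The tables are guidelines, nothing forbids reducing or stopping, and the literal result is silence on the dose level. Nor are such patients unsupervised: Sponsor contact is built into DLT cases, combination holds and extra cycles, and Section 4.3.2 halts enrollment after two possibly related non-hematologic Grade 4 events. These measures reduce the risk but set no dose for an ordinary rash, so the wording still needs correcting.

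It is also fair that 3.5 overstates the reach. It counts any Grade 3 or higher rash, combination enrollment was already under way at Amendment 7, and how the reported term rash maps onto this table's categories is unknown.

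**Conclusion.** The point holds as a minor safety-wording correction. In four rows the lead-in contradicts the steps below it. Followed as written, a Grade 4 or recurrent rash that has improved at the 2-week check has no stated reduction or discontinuation, and the decision passes to the Investigator, with Sponsor consultation in DLT and combination-hold cases. The number affected is probably small and may be zero. The patient figures assume that the monotherapy rash rate carries over to the combination and that planned enrollment is reached.

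One might also infer that the descriptive primary endpoint on dose reductions is distorted. With so few patients, any effect on that summary is probably small, and no bias claim is made.

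**What to change.** In all four rows, end the reassessment sentence with a full stop and replace the conditional phrase with: *Resume, reduce or discontinue camidanlumab tesirine by occurrence and time to improvement, as follows:*

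In the same rows, reword the existing *Otherwise* discontinuation lines to: *If improvement to ≤Grade 1 or Baseline does not occur, permanently discontinue camidanlumab tesirine.* There are five: non-blistering Grade 3 second occurrence, non-blistering Grade 4 first, blistering Grade 2/3 first and second, and blistering Grade 4 first. This second change is needed because the timed steps cover improvement before the next dose or more than 21 days after a missed one, but not the interval between. Once the lead-in is neutral, an unchanged *Otherwise* would literally force discontinuation of a rash that improves in that interval. For the same reason, add no such line to the Grade 3 non-blistering first occurrence. The dose for that interval stays with the Investigator under Section 6.6.1.

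The cost is one phrase in four rows and one line in five places at the next amendment. No assessment is added and the SAP does not change.
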